## **2.5. Statistical Interim analyses and stopping guidance**

There are no planned interim analyses or stopping guidance for this trial.

## **2.6. Timing of final analysis**

Analysis will be conducted following the final participant's 28 Week follow-up visit.

## **2.7. Timing of outcome assessments**

Outcomes are being assessed at baseline and at a follow-up date which is at 26 weeks for the control group and 28 weeks for the intervention group. For the Goal Attainment Scale (GAS), there is an additional follow-up at 12 weeks. Data for follow-up will be considered within window if it collected within two weeks of the expected date of collection. However, for this feasibility study, all data will be

used regardless of whether it is within window and a proportion of data being collected within and outside of the window will be reported.

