# 6. Study design

The study is a multi-centre, pilot cluster RCT of a rehabilitation programme intervention with embedded qualitative process evaluation. The PWD who have had a fall in the last six months are the patient participants; unpaid family members or friends of the patient participant are the carer participants. Patient participants and carer participants will be recruited in pairs, undertake the intervention, receive follow-up assessment at 28 weeks post-baseline assessment for the control group and 26 weeks after the initial assessment for the intervention group. The point at which followup assessment occurs varies between the control and intervention groups due to the assessment visits taking place for the intervention group during week 1 (see table 3). Each study site (cluster) will be randomly allocated to receive either the intervention or usual care. The intervention will include an assessment to identify any actions which need to be carried out to reduce the risk of falling or improve independence. This will be followed by a 12 week programme of activities facilitated by a team of therapists. Additional (booster) sessions will take place up to 6 months. The activities will be targeted at achieving personal goals chosen by the participants. We will follow participants up at 6 months to measure their independence in daily activities, mobility, fear of falling, falls, whether they achieved their goals, quality of life, caregiver burden and the health services and care they required. At the end of the trial we will know whether we should carry out a full trial to assess whether the intervention works and is good value for money.

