#### 7.6. Baseline Assessments and Data

Baseline data for PWD and their informal carers consenting to the study will be collected by a clinical researcher within two weeks of confirmation of eligibility. For PWD, this will include the DAD, EQ-5D-5L, QOL-AD, Short-FES-I and Timed Up and Go test. GAS will be collected by the intervention therapist at baseline for those randomised to the intervention (Table 2). Informal carers will be asked to complete EQ-5D-5L proxy, QOL-AD proxy, HUQ, EQ-5D-5L and ZBI (Table 2).

After the baseline assessment, the clinical researcher will inform the central research team. If the participant is in the intervention arm, the referral will be sent to the intervention team using a structured referral form with details of the baseline assessment of the PWD and the unpaid carer. The intervention team will then arrange an initial intervention assessment within two weeks. If the participant is in the control arm, usual care will continue.

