#### 7.7. Follow up Assessments

The clinical researcher will carry out a second visit to repeat most of the outcome measures completed at baseline with the PWD and their informal carer (see Table 2). For those in the intervention arm, this will take place 26 weeks after the start of the intervention. For those in the control arm, this will take place 28 weeks from baseline. The HUQ will also be completed at three months follow up by phone call. A fidelity checklist will be used to measure intervention fidelity.

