**Table 20- Proportion of Follow-Ups Occurring Within Window**

	Maintain Group		Control Group	
	N	n (%)	N	n (%)
Deviations- Timing of Visits				
Proportion of Follow-Ups Occurring Within Allowed Window at Final Follow-Up				

For all tables:

N = Total Number of Responses (Denominator)

n = Number whom the given option applied to (Numerator)

SD = Standard Deviation

IRR = Incident-Rate Ratio

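### SAP 2.7 reverses the two arms' final follow-up times relative to protocol v3.0 and gives no time origin, so the in-window proportions would be misreported unless the schedule has since been amended

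*SAP*

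**What the plan says.** SAP 2.7 sets the final outcome assessment "at a follow-up date which is at 26 weeks for the control group and 28 weeks for the intervention group". It names no starting event for either count. It then defines timeliness: "Data for follow-up will be considered within window if it collected within two weeks of the expected date of collection". The same section says that every observation will be analysed whether or not it meets the window, and that the split between in-window and out-of-window data will be reported. SAP 3.2 repeats that out-of-window visits will be given as a proportion. SAP Table 20 has one row, by arm: "Proportion of Follow-Ups Occurring Within Allowed Window at Final Follow-Up".

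Protocol v3.0 section 6 says that participants will "receive follow-up assessment at 28 weeks post-baseline assessment for the control group and 26 weeks after the initial assessment for the intervention group", and attributes the difference to the intervention arm's assessment visits in week 1. Section 7.7 repeats the assignment: "For those in the intervention arm, this will take place 26 weeks after the start of the intervention", and "For those in the control arm, this will take place 28 weeks from baseline". On the gap between baseline and the start of the intervention, section 7.6 says: "The intervention team will then arrange an initial intervention assessment within two weeks".

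SAP section 6 lists protocol version 5.0 (May 2024) as the related document. The protocol reviewed here is version 3.0 (08/11/2023).

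**The concern.** The SAP uses the protocol's two numbers with the arms exchanged. Because the window is defined around the target date, an exchanged target moves the window. The only targets that SAP 2.7 supplies are the exchanged ones, so a programmer working from the SAP and one working from protocol v3.0 would produce different Table 20 figures from the same visit dates.

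What is at stake is the description of how punctually each arm was followed up. Planners of the full trial may read that row when they set visit windows and staffing. Because the shift need not be the same in both arms, it could also suggest an arm difference in timeliness that did not occur.

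**Working it through.** **Inputs**
- Protocol v3.0 targets (sections 6 and 7.7): control = baseline + 28 weeks; intervention = start + 26 weeks.
- Lag L from baseline to the initial intervention assessment (section 7.6): taken as 0 to 2 weeks.
- SAP 2.7 targets: control 26 weeks, intervention 28 weeks, origin not stated.
- Window (SAP 2.7): target ± 2 weeks.

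**Step 1. Can the SAP's targets be obtained from the protocol?**
- Control: the only origin the protocol gives is baseline, and the target is 28. The SAP's 26 is not reproduced.
- Intervention, counted from its start: the target is 26. The SAP's 28 is not reproduced.
- Intervention, counted from baseline: the target is 26 + L, which is 26 to 28. The SAP's 28 is reproduced only when L = 2.

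**Step 2. Windows, in weeks**

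| Arm and origin | Protocol v3.0 | SAP 2.7 | Shared |
|---|---|---|---|
| Control, from baseline | 26–30 | 24–28 | 26–28 |
| Intervention, from start | 24–28 | 26–30 | 26–28 |
| Intervention, from baseline, L = 0 | 24–28 | 26–30 | 26–28 |
| Intervention, from baseline, L = 1 | 25–29 | 26–30 | 26–29 |
| Intervention, from baseline, L = 2 | 26–30 | 26–30 | 26–30 |

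For control, a visit exactly on the protocol date (week 28) falls on the last day of the SAP window, and any later visit counts as out of window. A visit at week 25, which is 28 − 25 = 3 weeks early under the protocol, counts as in window.

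**Step 3. Illustrative size**

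Neither document gives the spread of visit dates, so this step rests on assumptions. Let X be the visit date minus the protocol target, in weeks, with X ~ Normal(0, SD).
- Share in the protocol window: P(−2 < X < 2) = 2Φ(2/SD) − 1.
- Share in the SAP control window, which sits 2 weeks earlier: P(−4 < X < 0) = 0.5 − Φ(−4/SD).
- Share in the SAP intervention window counted from start: P(0 < X < 4), equal to the control figure by symmetry.
- Share in the SAP intervention window counted from baseline with L = 1: P(−1 < X < 3).

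| SD (weeks) | Protocol window | SAP control | SAP intervention, from start | SAP intervention, from baseline, L = 1 | Same, L = 2 |
|---|---|---|---|---|---|
| 0.5 | 100% | 50% | 50% | 98% | 100% |
| 1 | 95% | 50% | 50% | 84% | 95% |
| 1.5 | 82% | 50% | 50% | 72% | 82% |
| 2 | 68% | 48% | 48% | 62% | 68% |

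If visits run 1 week late on average with SD 1, the protocol window captures 84%. The SAP control window then captures P(−4 < X < 0) = 16%, and the SAP intervention window counted from start captures P(0 < X < 4) = 84%.

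An artefactual arm difference can therefore arise in two ways: visits centred on the target with the intervention count running from baseline (at SD 1 and L = 2, 50% control against 95% intervention), or visits running late with the count from start (16% against 84%). With visits centred on the target and the count from start, both arms are understated equally and no difference appears.

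**The case against.** Several points on the other side stand.

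- **The window excludes nobody.** All data are analysed irrespective of timing. A reader might infer that the reversal biases the treatment comparison or the stop/go decision; the documents do not support that. Timeliness is not among the three feasibility outcomes in SAP 5.1, and Table 20 presents it as visit-timing deviations.
- **The governing protocol was not seen.** The SAP cites v5.0. Its schedule already departs from v3.0: Goal Attainment Scaling gains a 12-week assessment, and Tables 9 and 10 report a frailty score and a comorbidity index that v3.0 does not list. A changed follow-up schedule is possible, so a transposition is likely but not proven.
- **The intervention half is not established.** Counted from baseline with the full two-week lag, the SAP's 28 weeks and the protocol's 26 weeks are the same date.
- **The visit-time SDs are assumed.**

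A reader might also infer that the SAP contradicts itself whichever protocol applies, because SAP 2.6 and 5.1 refer to week 28 without separating the arms. That is weak. Protocol v3.0 uses week 28 as a shared visit label in Table 3 and section 8.4 while setting arm-specific timing elsewhere. Nor is it a fault that the two arms' clocks start at different events: the protocol chose this and explains it.

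What the objection does not remove is the control arm. Under v3.0 there is no origin from which 26 weeks is the control target, and the SAP states no origin for either arm.

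**Conclusion.** The discrepancy is real and of minor to moderate importance. SAP 2.7 reverses the assignment that protocol v3.0 states twice and omits the time origin. If v5.0 left the schedule unchanged and SAP 2.7 is programmed as written, the control window is two weeks too early and shares only half of its four-week width with the protocol window. The intervention window is out by 0 to 2 weeks, depending on the unstated origin and the lag.

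Under the assumed SD of 1 to 1.5 weeks, with visits centred on the protocol date, the reported control in-window share would be about 50% instead of 82% to 95%. That range illustrates the mechanism; it is not a forecast. The consequence is limited to the timeliness proportions in SAP 3.2 and Table 20.

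**What to change.** Check SAP 2.7 against the current approved protocol and reconcile the two. State each arm's target week and the event from which it is counted, and derive the window, the SAP 3.2 proportion and Table 20 from those dates. If v5.0 did change the schedule, SAP 2.7 should say so and still give the origins.

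An optional addition is a Table 20 row giving weeks from baseline to follow-up (mean, SD) by arm, so that late starts of the intervention are visible. It is not needed to resolve the discrepancy.

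The cost is one corrected sentence in the SAP, plus one table row if wanted. No new data are needed. The change should be made before Table 20 is programmed.

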### **3. Statistical Principles**

#### **3.1. Confidence intervals**

Ancillary analysis is being performed on potential definitive trial outcomes and both mean differences and 95% confidence intervals will be reported for these outcomes for information on potential effectiveness. As this is all exploratory analysis, no p-values will be reported.

#### **3.2. Intervention adherence and protocol deviations**

For the purpose of this feasibility study, there is no deemed intervention adherence, but the number of visits that participants receive will be reported as part of the feasibility outcomes. Visits occurring out of window will also be reported as a proportion. Other protocol deviations will be reported by line-listing.

#### **3.3. Analysis populations**

For all analysis of outcome measures within this trial, an intention-to-treat approach will be implemented, except for analysis of safety and harms data, where an as-treated approach will be used. For a participant to be included within the safety population data, they must have received at least one intervention session to be considered within the intervention group for analysis.

Data for these analyses will use observed data only, with no use of imputation planned as part of the analysis.

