#### 7.3. Randomisation

Participating services (clusters) will be randomised in a 1:1 ratio to receive either the intervention plus usual care (intervention arm) or continue with usual care services (control arm). Randomisation will be undertaken based on computer-generated random numbers with no stratification factors.

After the baseline assessment, the clinical researcher will inform the central research team. If the participant is in a service (cluster) that is randomised to the intervention arm, the research team will send a referral to the intervention team using a structured referral form with details of the baseline assessments of the PWD and unpaid carer. The intervention team will then arrange an initial intervention assessment within 2 weeks.

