#### 8. Maintain Intervention

### 8.1. Description of the Intervention

The Maintain intervention is a multidisciplinary complex intervention which is delivered in the patient participant's home. The intervention will be personalised to each participant, taking into account their physical abilities, their preference for activities and goals agreed by the therapist, the patient participant and their unpaid carer. The number of sessions the participant receives will also be tailored to their needs. The first two sessions will be assessment sessions which will be followed by up to 19 therapy sessions delivered over 12 weeks and booster sessions at 16 weeks, 20 weeks and 24 weeks. An intervention manual will detail the assessment and therapy procedures for the professionals.

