### Serious adverse events (SAE)

All deaths (from any cause) and hospitalisations due to falls, fractures or musculoskeletal injury will be recorded. Other SAEs will not be recorded or reported. Only related SAEs will be subject to expedited reporting.

Causality of reportable SAEs will be assessed by the site PI (or authorised delegate). All SAEs which are possibly, probably or definitely related to the intervention will be categorised as 'related'. If the PI or delegate is unable to assign causality within 24 hours of the site becoming aware of the event, the SAE will be treated cautiously and subjected to expedited reporting.

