### 5.6. Harms

All harms that have been collected shall be reported as a total number that have occurred in the duration of the trial, and then reported by group on an as-treated basis.

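### Harms are grouped as treated, so intervention-site participants who never have a session leave that arm with their events, which tends to favour the intervention

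*SAP*

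**What the plan says.** SAP 3.3 sets the general rule and its exception in one sentence: "an intention-to-treat approach will be implemented, except for analysis of safety and harms data, where an as-treated approach will be used". It then gives the entry condition for the intervention group in the safety data: "they must have received at least one intervention session to be considered within the intervention group for analysis". Section 5.6 plans two summaries. The first is an overall count: "All harms that have been collected shall be reported as a total number that have occurred in the duration of the trial". The second is a breakdown of those harms, "then reported by group on an as-treated basis".

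The protocol supplies the rest:

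- **Events recorded** (8.3, Serious adverse events): "All deaths (from any cause) and hospitalisations due to falls, fractures or musculoskeletal injury will be recorded". Other serious events are not recorded.
- **Wait before the first contact** (7.3): after baseline, at intervention sites only, "The intervention team will then arrange an initial intervention assessment within 2 weeks".
- **What might count as a session** (8.1): "The first two sessions will be assessment sessions". The SAP does not define an intervention session.
- **Comparison principle** (9.4): outcomes are compared by the arm to which the site was randomised. The protocol version supplied (3.0) sets no as-treated population for harms. The SAP lists version 5.0 as its companion, which was not available here.

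The SAP appendix contains no shell table for harms.

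**The concern.** The entry condition applies to one arm only. A control participant is counted without any condition, whereas a participant at an intervention site must first reach a session. The recorded harms are the kind of event that can prevent this. Someone who dies before the first visit can never have a session. Someone admitted with a fall or fracture may not have one either, because sessions take place at home. Membership of the intervention group therefore depends partly on the outcome being tabulated.

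The rule is also incomplete. It says who is in the intervention group but not where an intervention-site participant without a session goes. Such a person could be left out of both groups or added to control. Two analysts could follow the SAP correctly and produce different harms tables.

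The Trial Steering Committee also acts as the data monitoring committee, looks at serious events for patterns, and discusses progression to a full trial. A by-group harms report that depends on who survived to a first visit is a weak basis for judging safety in the larger trial.

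**Working it through.** The documents give no event rate or precision target for harms, so there is no planned figure to reproduce. The check has three parts.

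**1. What moves under the rule.** SAP 3.3 classifies participants. It starts no clock at the first session.

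| Intervention-site participant | Group under SAP 3.3 | Where the event goes |
|---|---|---|
| Event before the first session, session held later | Intervention | Stays |
| Death before the first session | Not intervention | Leaves |
| Fall or fracture admission, never has a session | Not intervention | Leaves |
| No event, never has a session | Not intervention | Only the denominator changes |

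The raw event count in the intervention group can therefore only fall or stay the same. A proportion can move either way.

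**2. Expected size.**

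Inputs from the documents: 30 participants per arm (SAP 2.3), 28 weeks of follow-up from baseline (protocol 7.7, control arm), and a planned gap of at most 2 weeks (protocol 7.3), which is 2/28 = 7.1% of follow-up.

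Assumptions not in the documents: the same constant hazard in both arms, a 28-week risk p of 5% to 30%, and the extreme case that everyone with a pre-session event never starts.

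Formulas for a gap of w weeks:

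- hazard λ = −ln(1 − p)/28
- probability of an event in the gap q = 1 − exp(−λw)
- expected participants leaving with an event = 30q
- intervention proportion = (30p − 30q)/(30 − 30q)
- control proportion = p if never-starters are dropped, or (30p + 30q)/(30 + 30q) if they are moved to control

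For p = 10% and w = 2, 30q = 0.225. The intervention proportion is 2.775/29.775 = 0.0932. The ratio is 0.0932/0.10 = 0.932 if dropped. If moved, control is 3.225/30.225 = 0.1067 and the ratio is 0.874.

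| 28-week risk | Events per arm by allocation | Leaving (2-week gap) | Ratio, dropped | Ratio, moved | Chance of at least one event in the gap |
|---|---|---|---|---|---|
| 5% | 1.5 | 0.110 | 0.930 | 0.870 | 0.104 |
| 10% | 3.0 | 0.225 | 0.932 | 0.874 | 0.202 |
| 20% | 6.0 | 0.474 | 0.936 | 0.881 | 0.380 |
| 30% | 9.0 | 0.755 | 0.940 | 0.889 | 0.534 |

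With a 1-week gap, 0.055 to 0.380 leave, and the ratios are 0.965 to 0.970 (dropped) and 0.933 to 0.943 (moved). By allocated arm the ratio is 1.00 throughout. If every participant with a pre-session event later has a session, nothing moves and it stays at 1.00.

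**3. What one or two participants do at this size.** Start from 3/30 v 3/30, a ratio of 1.00.

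- One never-starter with an event: 2/29 v 3/30 = 0.069/0.100 = 0.69 if dropped, or 2/29 v 4/31 = 0.069/0.129 = 0.53 if moved.
- Two never-starters without events: 3/28 v 3/30 = 0.107/0.100 = 1.07 if dropped, or 3/28 v 3/32 = 0.107/0.094 = 1.14 if moved.

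**The case against.** The strongest reply is that little rests on this table and that an as-treated view has a proper use. Events before any session cannot have been caused by the sessions, so grouping by treatment received helps with attribution. The protocol calls the trial low risk and says that safety is not an outcome measure. No safety item appears in the progression criteria, and no test or interval is planned for harms. The overall total in SAP 5.6 keeps every event in view, and the participant flow diagram gives reasons for withdrawal and loss. All of this stands. It limits the consequence and justifies keeping the as-treated view. It does not justify an entry condition on one arm as the only planned grouping of recorded harms.

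A reader might also infer three stronger points that the documents do not support:

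- **Every pre-session event leaves the intervention arm.** It does not. Someone admitted before the first session who later has one stays in the arm, with the event.
- **The plan has no other between-arm comparison relevant to safety.** Falls are compared by intention-to-treat, with a mixed Poisson model (SAP 5.2) and an incidence rate ratio (SAP Table 16).
- **The intervention must look safer.** This is certain only in the weak sense that its raw count cannot rise. Event-free never-starters push the proportion the other way.

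**Conclusion.** The point holds as a moderate defect of definition and grouping. The rule puts a condition on one arm that the recorded harms can prevent a participant from meeting, and it leaves never-starters without a stated place. The usual direction favours the intervention.

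The expected distortion is small: fewer than one participant with an event, and a ratio of 0.93 to 0.94 (dropped) or 0.87 to 0.89 (moved) where the truth is 1.00. Those figures rest on an assumed 28-week risk of 5% to 30%, a constant and equal hazard, a 2-week gap, and every pre-session case failing to start. The last is an upper extreme. A first contact later than planned, or a reading under which assessment visits do not count as sessions, would lengthen the gap and enlarge the shift. Even so, with 30 per arm a single reclassified event visibly changes the by-group picture, so a small expected value is not sufficient reassurance.

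**What to change.** In SAP 3.3 and 5.6:

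1. Make the main descriptive harms table by the site's allocated arm, for all consented patient participants, from baseline to final follow-up. Give participants with at least one event, number of events and person-time, and add a shell table to the appendix.
2. Keep the as-treated view as a supplement for attribution, flagging events before the first session.
3. Define an intervention session, including whether the two assessment visits count.
4. State where never-starters are placed in the as-treated view, and report their number and their events.

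Person-time also needs one agreed follow-up schedule. SAP 2.7 gives 26 weeks for control and 28 for intervention. Protocol sections 6 and 7.7 give 28 weeks from baseline for control, and 26 weeks from the initial assessment or start of the intervention for the intervention arm. These passages must be reconciled.

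The cost is SAP wording and one extra table, with no new visits or outcome measures. The drawback is that the allocated-arm table will include some events that the sessions could not have caused; the supplement makes these visible.
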